- The force will be measured by a force gauge and reactivated every 4 weeks maintaining constant force of retraction all over the retraction phase.

➤ **Follow up visits**

Patients will be asked to attend for follow up sessions every 4 weeks for:

- Evaluation mini-screws stability.
- Replacement of the power chain to maintain a force of 160 gm per side.
- Reactivation of the T-loop by further distal activation and cinch back if needed.

➤ **Criteria for discontinuing or modifying the allocated intervention:**

In cases of prolonged swelling or pain related to the mini-screw the patient will be given strict oral hygiene measures and the beginning of retraction will be postponed for three weeks.

In cases of loose or broken mini-screws, the screw will be removed and replaced.

➤ **Retraction records**

Following retraction of the anterior segment, patients will be referred to the same radiology center to acquire the final CBCT to assess the movement and inclination of anterior teeth.

➤ **Materials**

- American Orthodontics Brackets, Roth prescription, 0.022 slot size.
- American Orthodontics Elastomeric power chains.
- American Orthodontics Elastomeric O-ties.
- American Orthodontics Ligature wire.
- Mini-screw (1.6- by 8-mm, bracket head design; Dual Top Anchor System, Jeil Medical Corporation, Seoul, Korea).
- American Orthodontics Arch wires.
- American Orthodontics Molar bands/tubes.
- Crimpable hooks (Dentos Inc.)

D] Outcomes

[figure not shown]
Primary outcome: is to monitor the changes in the anterior teeth position (final anterior teeth tip, torque and vertical position) in association with each technique after retraction

Secondary outcomes: are to detect the presence of any root resorption associated with the different methods used for anterior segment. All outcomes

will be assessed as the difference between T0 at the start of anterior segment retraction after full canine retraction and T1 after complete space closure.

E] Participant timeline:

1. The principle investigator will screen the potential patients through careful clinical examination of patients at the orthodontic department, Faculty of Oral and Dental Medicine at The Future University of Egypt.
2. All recruited patients must fulfil the previously mentioned inclusion and exclusion criteria.
3. Every participant will be asked to sign an informed consent before the beginning of the study.

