Numerical data will be tested for the normal assumption using Kolmogorov Smirnov and Shapiro Wilk tests. If normal distribution was found; therefore, data will be statistically described in terms of mean \pm standard deviation (\pm SD). Student t test will be used to compare between the study groups for independent samples in comparing normally distributed data. Paired t test will be used within group comparisons in comparing normally distributed data and Two-sided p values less than 0.05 will be considered statistically significant.

F] Recruitment strategy:

The principal investigator will recruit the patients from the clinic of Orthodontic department, Faculty of Oral and Dental Medicine- Future University.

Screening of patients will continue until the total number of participants for the study is collected.

II) Assignment of interventions:

A] Sequence generation:

The supervisor of the study will apply Computer generated random numbers to randomly assign patients to Group A (Friction) or B (Frictionless) using Microsoft Office Excel 2007 sheet. and will write the patient numbers in the first column, and will select function RAND()to generate the randomization number in the second column. These numbers will be sorted according to the randomization number so the first column numbers will be randomly distributed.

B] Allocation concealment mechanism:

The supervisor of the study will write the randomization numbers of the patients in opaque white papers folded three times to form sealed envelopes and store it inside a box. Then will keep the Codes for randomization at the secretary office.

C] Implementation:

At time of intervention, the main operator will send the patient to the secretary office. Then, the assigned employee will open the box and ask the patient to select one envelope. the main operator will assign each participant for the corresponding intervention either (friction or frictionless group) according to the list of codes of randomization.

Assignment to either intervention will occur before leveling and alignment stage.

D] Blinding:

Blinding of the operators: Blinding will not be possible for the operators during the application interventions and during the follow up visits. The principal operator is responsible for assigning subjects to interventions according to the concealed allocation, appliance activation at follow up visits.

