Blinding of the outcome assessors: It is a single blinded study, the outcome assessors only will be blind. The patients name will be sealed from pre and post records. Then two assessors will carry on, blindly and independently, the measurements and analysis of the study.

III) Data collection, management and analysis:

A] Data collection methods:

Primary outcome:

1. *Anterior teeth torque, extrusion/intrusion:* will be assessed by the principle investigator via CBCT taken before and after the completion of retraction. The principal investigator identified the landmarks, reference lines and planes, then interpreted the measurements in degrees and millimeters.

2. *Anterior teeth tip:* will be assessed by the principle investigator via CBCT taken before and after the completion of retraction.

Secondary outcomes:

1. *Root resorption:* will be assessed by the principle investigator via CBCT taken before and after the completion of retraction. The resorption will be identified using scoring system of Levander and Malmgren[21] that classifies it into 5 grades: 0: no root resorption; 1: mild resorption, with the root of normal length and only an irregular contour; 2: moderate resorption, with small areas of root loss and the apex having an almost straight contour; 3: severe resorption, with loss of almost one third of root length; and 4: extreme resorption, with loss of more than one third of the root length.

B] Data management:

A colleague outside the research team will enter the data and organize it in excel sheets in the computer of the orthodontic department.

Data will include all photographs, models and radiographs.

C] Statistical Analysis:

- The principle investigator will be responsible for the extraction of the required data from the CBCT taken before and after retraction. The data will be sent to a specialized statistician.

- The specialized statistician will be responsible for the statistical analysis of the study by:

1. Presenting the data as mean, standard deviation (SD) and Standard error (SE) values.

2. Using Paired t-test to compare between the friction and the frictionless group of retraction as well as to compare between the pre-and post -treatment data for each group.

3. Using Anova test to determine the rate of anterior segment retraction.

4. Statistically evaluate the patient acceptance for both techniques.

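### No suitable analysis is specified for the ordinal root-resorption grade; by default it falls under mean/SD/SE and t-test rules that can equate many mild changes with a few severe ones

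*Combined protocol and SAP*

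**What the plan says.** The Outcomes section (part I, D) gives one secondary outcome. Its stated aims "are to detect the presence of any root resorption associated with the different methods used for anterior segment". The next sentence covers all outcomes without exception: they "will be assessed as the difference between T0 at the start of anterior segment retraction after full canine retraction and T1 after complete space closure".

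The Data collection methods section (part III, A) names a scoring system "that classifies it into 5 grades: 0: no root resorption; 1: mild resorption" and runs up to "4: extreme resorption, with loss of more than one third of the root length". Grade 1 is a contour change with root length preserved. Grade 3 is a loss of close to one third of the root.

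Two sections govern the analysis, and neither mentions root resorption:

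- Statistical Methods (after the sample size calculation) tests numerical data for normality and then says: "If normal distribution was found; therefore, data will be statistically described in terms of mean". Its t-tests are limited to normally distributed data. It names nothing for data that fail the check.
- Statistical Analysis (part III, C) has no such condition. It lists "Presenting the data as mean, standard deviation (SD) and Standard error (SE) values" and then "Using Paired t-test to compare between the friction and the frictionless group of retraction", with the same test for pre-post comparison within each group.

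The documents contain no frequency table, median, rank test, ordinal model or exact test. They do not say how the grades of several teeth become one value per patient.

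**The concern.** The grades are ordered, but the distances between them are not equal. Moving from 0 to 1 means an irregular contour on a root of normal length. Moving from 3 to 4 means passing one third of the root length. Subtraction and averaging count both as one unit.

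The two analysis sections lead to different faults. Under Statistical Analysis the grade change is averaged and t-tested. Under Statistical Methods it would normally fail the normality check and have no planned analysis, leaving the statistician to choose a method after seeing the data. On either reading, the comparison of resorption between the two mechanics lacks a pre-specified result that answers the question asked.

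**Working it through.** **1. The plan's own figure.** The only sample size calculation concerns incisor-edge distance in mm: difference 1.0, SD 0.76, two-sided alpha 0.05, power 0.80. By the normal approximation, n = 2(1.96 + 0.84)² × 0.76² / 1.0² ≈ 9.1, rounded up to 10 per group. With the noncentral t distribution, power at 10 is 0.795. The stated 10 reproduces, with 15 planned to allow for dropout. It says nothing about root resorption, which has no power calculation.

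**2. Would the grade pass the normality condition?** The documents give no resorption rates, so every distribution here is an assumption. Four sets of probabilities for a change of 0, 1, 2 or 3 grades were used. Shapiro-Wilk was applied to 3,000 samples of 15 from each, and samples with all values identical were counted as failing.

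| Assumed change 0/1/2/3 | Normality rejected, n = 15 |
|---|---|
| 0.93/0.05/0.02/0 | 100% |
| 0.80/0.15/0.05/0 | 100% |
| 0.50/0.35/0.10/0.05 | 99.6% |
| 0.30/0.40/0.20/0.10 | 90% |

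With the grade itself, at assumed frequencies of 45/30/15/7/3% for grades 0 to 4, rejection was about 97% at n = 15 and 81% at n = 10.

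**3. Is the t-test's error rate wrong?** Both arms were drawn from the same distribution at a nominal 0.05, with 20,000 runs for the independent t-test and 4,000 for Mann-Whitney. Ranges are over the four distributions.

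| n per arm | Independent t | Mann-Whitney |
|---|---|---|
| 10 | 0.004-0.050 | 0.003-0.043 |
| 15 | 0.012-0.049 | 0.012-0.048 |

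Neither test is inflated, and both are very conservative when resorption is rare. In three assumed scenarios with a true difference, power at 15 per arm was 0.72, 0.48 and 0.39 for the t-test and 0.68, 0.48 and 0.40 for Mann-Whitney.

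**4. What the mean change conveys.** Take two hypothetical arms of 15:

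- Arm X: 8 patients worsen by one grade and 7 are unchanged. Mean = 8/15 = 0.53. SD = √[(8 − 15 × 0.533²)/14] = 0.52.
- Arm Y: 2 patients worsen by four grades and 13 are unchanged. Mean = (2 × 4)/15 = 0.53. SD = √[(32 − 15 × 0.533²)/14] = 1.41.

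The difference in means is 0, so t = 0 and p = 1.00. In arm Y, two patients went from no resorption to loss of more than a third of the root. In arm X, resorption progressed in more than half the patients, by one grade each. The mean and the t-test report the arms as equal.

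**5. How the alternatives behave on the same data.** Mann-Whitney gives p = 0.067. For any worsening, 8/15 against 2/15, Fisher's one-sided tail is [C(15,8)C(15,2) + C(15,9)C(15,1) + C(15,10)C(15,0)]/C(30,10) = (675,675 + 75,075 + 3,003)/30,045,015 = 0.0251. The two-sided p is twice that, 0.050, because the arms are equal in size. Both tests respond to how many patients worsened, and neither flags the two severe cases. Only a table of grades, with the count at grade 3-4, shows those.

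**The case against.** The strongest reply is that no sentence tells anyone to subtract and average resorption grades. The rule arises from joining general wording in two sections. Assessing a difference between time points can mean change in a loose sense, the aim of detecting any resorption suggests a yes/no result, and Statistical Methods confines itself to numerical data. This stands as far as it goes: a reader might infer an explicit instruction about this outcome, and there is none. But if the general wording does not apply to the grade, nothing else does, and the outcome has no analysis at all.

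A reader might also infer that the t-test p-value would be invalid or the result uninterpretable. The simulations do not support that, since error rate and power are close to those of the rank test.

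Nor would severe cases be invisible. The planned SD would partly expose them (0.52 against 1.41 in the example), although an SD does not tell a clinician how many patients reached which grade.

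Finally, this is one secondary outcome with no power calculation, and the primary comparison is unaffected. That limits the weight of the point but does not remove it.

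**Conclusion.** The point holds as a gap with an unsuitable default. The only secondary outcome is ordinal, no ordinal or categorical method is provided, and the general rules lead either to a mean grade change or, in roughly 90% or more of samples of 15 under the assumed distributions, to no permitted test. The harm lies in what is estimated. A mean change can equate 8/15 mild with 2/15 extreme worsenings, and it does not answer whether any resorption occurred.

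The size rests on assumed grade distributions and a constructed example, because the documents give no resorption rates. The conclusion that no method is specified does not depend on those assumptions. The change should be made before analysis; it does not threaten the primary result. The paired t-test assigned to independent groups in the Statistical Analysis section is a separate defect.

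**What to change.** In the Statistical Analysis section (part III, C), exempt root resorption from the mean/SD/SE and t-test rules, and align the Outcomes and Statistical Methods sections with that. Then state:

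1. **One value per patient**, for example the worst grade among the measured anterior teeth, at T0 and at T1. T0 follows levelling, alignment and canine retraction, so resorption may already be present then. An unadjusted T1 grade would discard that information.
2. **A table of T0 and T1 grades by arm**, with the number of patients showing any worsening from T0 and the number at grade 3-4. This is the essential part, because no single test flags a few severe cases.
3. **A comparison of the independent arms**: Fisher's exact test on any worsening from T0, and/or an exact Mann-Whitney test on the T1 grade that takes the T0 grade into account, for example by stratification.

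A five-level proportional-odds model should not be relied on at 15 per arm, where sparse grades may make it unstable.

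The cost is a few sentences and one extra table, with no new data. The comparison remains unpowered and should be reported as descriptive. The statistician should confirm that the chosen SPSS release offers the stratified rank test if that option is taken.

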Research hypothesis:

The null hypothesis (H_0) of this research is that there's no difference between both frictionless and friction mechanics on anterior teeth position during anterior segment retraction following 1st premolar extraction

Primary objective (s):

Measuring changes in extrusion/ intrusion, tip and torque of anterior teeth following anterior segment retraction using frictionless vs friction mechanics.

Secondary objective:

Measuring the root resorption during anterior segment retraction using frictionless vs friction mechanics.

Study design:

This is a randomized clinical trial with two arms parallel group, and 1:1 allocation ratio. In one group, frictionless mechanics will be applied during anterior segment retraction while the other will receive frictional mechanics during retraction to compare the changes in anterior teeth position.

Material and Methods

I)participants, interventions, and outcomes

A] Study Setting:

The study will be performed in the clinic of the Orthodontic Department at the Faculty of Oral and Dental Medicine, Future University. The recruited sample is from the Egyptian urban and rural population.

B] Eligibility criteria:

➤ **Inclusion criteria:** for the participants include the following:

1. Female patients, Age range (13-25)
2. Bimaxillary protrusion requiring extraction of four first premolars and maximum anchorage.
3. Patients with fully erupted permanent teeth (not necessarily including the 3rd molar).
4. Good general and oral health.
5. Class I molar relation (Angle's classification)

➤ **Exclusion Criteria:** for the involved subjects include:

1. Patients suffering from any systemic diseases or syndromes or on anti-inflammatory medication interfering with tooth movement.
2. Patients with extracted or missing permanent teeth. (except for third molars).
3. Patients with badly decayed teeth.
4. Patients with any parafunctional habits.
5. History of previous orthodontics treatment.

C] Interventions:

➤ Medical History Questionnaire:

For every patient to exclude the presence of any systemic condition interfering with orthodontic treatment.

➤ Clinical Examination:

Oral structures will be examined to identify caries, fracture or missing teeth. Gingival tissues will be carefully examined for any gingivitis, periodontitis, recession or lesions.

➤ Diagnosis

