4. After patient's enrolment, each participant will be asked for pre-intervention records to ensure proper diagnosis.
5. The co-supervisor will randomly allocate the patients to one of the intervention groups.
6. Active intervention will start after proper leveling and alignment of the upper and lower arches and canine retraction.
7. The principle investigator will take pre-retraction records for every participant (T0).
8. In Friction mechanics group, Power chain will be used for anterior segment retraction while in Frictionless group, T-loop will be used for retraction.
9. Each patient will come every 4 weeks for the follow up visit, for appliance activation and impressions for interim records.
10. After complete space closure, the principle investigator will take post-retraction records for each participant (Tfinal).
11. The principle investigator will continue the normal treatment and achieve proper finishing for every patient after the end of the study.

E] Sample size calculation:

In a previous study by **Dincer et al.** [1], they compared the effect of frictionless mechanics via PG spring (Poul Gjessing spring) (Group I) and friction mechanics using coil spring (Group II). The mean change in distance between central incisor edge and x-axis was of 0.68mm and SD of 0.73 in Group I, while Group II was -0.32mm and SD of 0.79.

Sample size calculation was done based on that study using PS software output. A continuous response variable from independent Group I and Group II subjects was planned. In the previous study, the response within each subject group was normally distributed with standard deviation 0.76. If the true difference in the Group II and Group I means is 1.0, we needed to study 10 Group II subjects and 10 Group I subjects to be able to reject the null hypothesis. The population means of the Group II and Group I are equal with probability (power) 0.8. The Type I error probability associated with this test of this null hypothesis is 0.05. Considering drop out a sample size of 15 per group was planned (**Figure 1**).

[figure not shown]

Figure 1: Power curve for 2-sample t-test denoting the power of the study.

Statistical Methods

All statistical calculations will be done using computer program IBM SPSS (Statistical Package for the Social Science; IBM Corp, Armonk, NY, USA) release 22 for Microsoft Windows.

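### The plan names two incompatible tests for the between-arm comparison, and one of them, a paired t-test, does not fit unmatched parallel arms

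*Combined protocol and SAP*

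**What the plan says.** Two sections of the combined protocol and SAP prescribe the between-arm test.

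- **Statistical Methods** (after the sample size calculation): "Student t test will be used to compare between the study groups for independent samples in comparing normally distributed data". The paired test has a separate role there: "Paired t test will be used within group comparisons in comparing normally distributed data".
- **III) Data collection, management and analysis, C] Statistical Analysis, item 2**: "Using Paired t-test to compare between the friction and the frictionless group of retraction". The same sentence goes on to give the paired test to the pre/post comparison in each group as well, so it cannot be read as a within-group rule only.

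Three other places bear on which is right.

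- **Study design**: "This is a randomized clinical trial with two arms parallel group, and 1:1 allocation ratio".
- **II) Assignment of interventions**: patients are put in random order individually with a spreadsheet random-number function. At Implementation, staff "ask the patient to select one envelope". No matching, split-mouth or crossover feature is described.
- **Sample size calculation**: "A continuous response variable from independent Group I and Group II subjects was planned". The caption of Figure 1 reads: "Power curve for 2-sample t-test denoting the power of the study".

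Neither analysis section is given precedence.

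**The concern.** A paired t-test needs a natural link between each observation in one arm and one in the other. This design creates none. If item 2 were followed, the pairing would come from the order of rows in the data file, and three things would follow:

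- The p-value would depend on that arbitrary order.
- If dropout left unequal arms, patients without a partner would be discarded.
- The test carried out would not be the one the trial was sized for.

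Item 2 sits in the list addressed to the statistician who will do the analysis, so it could well be followed literally. Even if it is not, two conflicting rules on file leave the test for every primary outcome open to choice after the data are seen.

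**Working it through.** **Inputs.** All come from the Sample size calculation except the sidedness, which is in Statistical Methods: difference Δ = 1.0 mm; SD σ = 0.76 mm; α = 0.05, two-sided; target power 0.80; 10 per arm evaluable, 15 per arm planned. These values describe the vertical position of the central incisor edge. The plan gives no effect or SD for tip or torque, so the power figures apply to vertical position only.

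**1. Reproduce the plan's figure.** The SD agrees with the two group SDs quoted: √[(0.73² + 0.79²)/2] = √0.5785 = 0.761. With two independent groups and the normal approximation,

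n per arm = 2(1.960 + 0.842)² × 0.76² / 1.0² = 9.07, rounded up to 10.

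This matches the stated 10. With the noncentral t, the independent test at 10 per arm has power 0.795, in line with the stated 0.80.

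**2. Power under each rule.**

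- Independent test: noncentrality Δ / (σ√(1/n₁ + 1/n₂)), df = n₁ + n₂ − 2.
- Paired test on m = min(n₁, n₂) arbitrary pairs: unrelated patients have zero correlation, so the SD of a difference is σ√2. Noncentrality is Δ / (σ√(2/m)), df = m − 1.

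At 10 per arm both noncentralities equal 1.0 / (0.76 × √0.2) = 2.942. Only the degrees of freedom differ (18 against 9), so the critical value rises from 2.101 to 2.262.

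| Completers per arm | Independent: df, power | Paired: df, power | Patients discarded |
|---|---|---|---|
| 10 and 10 | 18, 0.795 | 9, 0.745 | 0 |
| 15 and 15 | 28, 0.935 | 14, 0.917 | 0 |
| 15 and 12 (assumed) | 25, 0.904 | 11, 0.835 | 3 |
| 15 and 10 (assumed) | 23, 0.870 | 9, 0.745 | 5 |

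The unequal rows are illustrations. The plan expects dropout ("Considering drop out a sample size of 15 per group was planned") but gives no rate or split between arms. For 0.80 power the paired rule would need 12 pairs, not 10.

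**3. How often the two rules disagree.** Normal data were simulated with 400,000 data sets per setting and one arbitrary pairing each, at Δ = 1.0. The tests fall on opposite sides of 0.05 in 9.35% of data sets at 10 per arm (7.1% significant by the independent test only, 2.2% by the paired test only). At 15 per arm the figure is 3.4% (2.65% and 0.8%).

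**4. Type I error (Δ = 0), same simulation.**

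| Per arm | Independent | Paired | Either significant |
|---|---|---|---|
| 10 | 0.0495 | 0.0494 | 0.0643 |
| 15 | 0.0502 | 0.0497 | 0.0620 |

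Each test holds its level alone, provided row order is unrelated to outcome. Choosing between them afterwards does not.

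**5. Sensitivity to row order.** As an extreme case, sorting both arms by outcome before pairing raises the paired test's type I error at 10 per arm to about 48% (20,000 simulated data sets). Nothing in the plan suggests this would be done. It shows only that the result depends on something the plan does not fix.

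**The case against.** The strongest reply is that the intent is easy to infer. Statistical Methods, the sample size text and the Figure 1 caption all point to the independent test. Item 2 alone dissents, in a sentence that merges the between-arm and pre/post comparisons. The valid test is therefore already in the plan, and the cost of the wrong one is small: under 2 points of power with 15 completers per arm, still well above 0.80, and type I error of about 0.062 there even if the test were picked afterwards. The larger losses rest on assumed dropout patterns.

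All of that is accurate, and it limits the size of the problem. It does not remove it. An inferable intent is not a prespecified rule, and item 2 is a direct instruction about the primary comparison. The sections also show other signs of not having been reconciled: SPSS release 22 in one and version 20 in the other, and a threshold of p below 0.05 in one and p at or below 0.05 in the other. These change no result but weaken the presumption that one section is meant to prevail.

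Two further remarks stand. Statistical Methods makes its t-test conditional on normality and names no between-arm method if that fails, so pointing to that section alone would leave a gap. And the lack of a suitable method for the ordinal root resorption grade is a separate, secondary matter that adds no weight here.

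**Conclusion.** The concern holds. Item 2 is wrong for the design, it contradicts Statistical Methods, and no text resolves the conflict. It should be corrected because the primary between-arm comparison lacks a single valid rule, not because the numerical damage is large. For vertical position, following item 2 costs about 5 points of power at 10 per arm and 2 points at 15. With the assumed 15/12 and 15/10 splits it costs about 7 and 12 points. Reporting whichever test is significant raises type I error to about 0.064 (10 per arm) or 0.062 (15 per arm).

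These figures assume normal outcomes with a common SD of 0.76, no correlation between patients in different arms, and row order unrelated to outcome. The planned sample size is unaffected: it was derived for the independent test and reproduces.

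**What to change.** - In section III C, item 2, remove the paired t-test as the between-arm test. State that the arms are compared on the patient-level T0-to-T1 change (the Outcomes section already defines all outcomes as that difference) with the independent-samples t-test. Keep the paired t-test for pre/post change within each arm only.
- State that this rule governs wherever the two analysis sections differ, and align the software version and significance threshold.
- To make the rule complete, say in advance what is done between arms if normality is doubtful, and how measurements on several anterior teeth are reduced to one value per patient.
- Separately, for the 0–4 root resorption grade, name a rank-based or ordinal between-arm comparison with counts per grade, and the rule for reducing tooth grades to one grade per patient. The plan names only t-tests, plus an ANOVA assigned to retraction rate.

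The cost is SAP wording only. Sample size, visits and measurements do not change.
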